Previous research suggests that the incidence of dementia and Alzheimer's disease (AD) is higher in those with prevalent cardiovascular disease (CVD), and is also associated with increased platelet activity. Whether the platelet abnormalities are related to a common atherogenic process or rather represent different inflammatory pathways is unclear and needs to be examined. In addition to their role in CVD,

platelets have been implicated in the pathology of AD at several levels. First, abnormal platelet activation markers are frequently observed in AD patients when compared with age-matched cognitively normal controls. Additionally, results in experimental animal models and postmortem human brains show that platelet markers accumulate in perivascular lesions. Since platelets contain A β and tau, which are the components of amyloid plaques and neurofibrillary tangles found in AD lesions, it is possible that platelets are contributors to lesion formation at earlier stages of the disease.

We hypothesize that the platelet phenotypes (already measured) in patients with CVD are associated with cognitive decline and our preliminary studies suggest that this is the case. Using data from the Framingham Heart Study, we recently demonstrated that platelet aggregation in cognitively unimpaired middle age subjects is independently associated to the risk of incident dementia even after adjusting for potential confounders suggesting that the detection of platelet phenotypes in patients with CVD could be used for the detection of risk of cognitive decline in this population.

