We designed the PACE clinical study initially to investigate platelet activity in PAD patients and the incidence of major adverse cardiac and limb events after lower extremity revascularization. PACE was set up to investigate the relationship between platelet activity and cardiovascular risk. Many studies suggest the overlapping nature of cardiovascular risk and dementia. Thus, we would like to extend findings that have established the link between heart disease and dementia to platelet activity and dementia. The comprehensive platelet characterization already performed would facilitate our study investigating the association between platelets and cognitive decline in this cohort of patients with established CVD. We will attempt to call all living participants and obtain telephone consent for the additional measure, assess vital status, and perform a validated survey of subclinical cognitive impairment in the PACE cohort with 2 previously validated neuropsychiatric tests that are frequently used in aging studies: TICS and Montreal Cognitive Assessment, MoCA. Both tests can be easily done remotely by trained personnel and are particularly good at detecting early subclinical impairment.

3. Specific Aims

Aim 1. To determine whether preoperative platelet activity measurements are independently associated with short-term cardiovascular events in PAD patients undergoing non-emergent lower extremity revascularization. We will characterize the platelet phenotype in 350 PAD patients before vascular surgery and use Cox proportional hazard models to determine the independent association of the platelet phenotype with risk of cardiovascular events in the first 30 days after surgery.

Aim 2. To determine whether postoperative platelet activity measurements are independently associated with long-term cardiovascular events in patients with established PAD. We will characterize the postoperative platelet phenotype following surgery and use Cox proportional hazards models to determine the independent association of the platelet phenotype with risk of long-term composite of myocardial infarction, stroke, or all-cause mortality with a mean follow-up of 2-years following vascular surgery.

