Aim 3. To investigate mRNA-microRNA co-expression profiles in patients with and without elevated platelet activity measurements. We will establish the relationship between differentially expressed microRNAs and their target mRNAs related to platelet activity and thus identify new diagnostic markers and potential therapeutic targets of increased platelet activity.

Aim 4. To investigate whether the platelet phenotype of patients with PAD associates with measures of cognitive impairment. We will contact participants enrolled in PACE to conduct a screening test for cognitive function via telephone and/or video-call using the MoCA and/or TICS tests. We will correlate these measures with already collected platelet activity measures.

4. Research Design

a. Recruitment

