written consent for future analysis, contact, and sample storage. Stored samples will not undergo further genetic testing. Consenting will take place in the hospital (in the preadmission testing or in the pre-operative holding area) or in a private office (in the vascular surgery or medical practice). Subjects will be given the opportunity to be contacted for future studies that they may qualify for as well. All subjects will be given a copy of the consent. A member of the research team will conduct the baseline interview with the subject and review the clinical history, demographic information, diet questionnaire, lifestyle assessment, medication use and adherence, with the individual. A case report form is attached as an appendix. All information including the consent will be kept under double lock and key at the PI's office in NYU Skirball 9th floor

c. **Methods**

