
There will be a follow-up component of this study that obtains blood and urine following surgery and at their first return visit following surgery. This will allow us to assess the change in platelet activity,

thrombin, coagulation and inflammatory markers during and following the perioperative period. This additional component would consist of a blood collection on postoperative day 2 (+/- 1 day). No more than 60 ml (≈4 table spoons) of blood will be collected at this time point. In addition, a blood collection will be obtained at the subjects' return visit following surgery to the vascular surgeon. No more than 60 ml (≈4 table spoons) of blood will be collected at this time point. The total blood drawn for the follow-up component would be no more than 120ml (8 tablespoons). This blood will be used for the different measurements of platelet activity, thrombin, coagulation and inflammatory markers. Data gathered from this component of the study will help understand the dynamic profile of biomarkers during and following the perioperative period.

Total amount of blood withdrawn will be no more than 180 ml (approximately 12 tablespoons or 40% of a standard blood donation). We believe this amount of blood is small and spread out over a month and therefore patient is at minimal risk. Blood collection at three different time points (before surgery, following surgery while still in the hospital, and at the subjects' first return visit to the vascular surgeon following surgery) will allow us to assess the dynamic change in platelet activity, coagulation and inflammation during the perioperative period. We believe that markers of clotting and bleeding will change during the course of surgery, and that some of these markers may be used to help predict the likelihood of developing a clotting or bleeding event following surgery. The long-term goal is to develop a clinically useful assessment of platelet activity, thrombin generation, coagulation and inflammation for risk stratification that may ultimately serve as a target for therapeutic intervention. The platform proposed will serve as a basis for future research and intervention, and hopefully, will have a great impact on subjects undergoing vascular surgery.

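### Aim 4 is to be analysed by correlating cognitive scores with platelet measures, and the available text states no adjustment for age

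*Combined protocol and SAP*

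**What the plan says.** Section 3, Aim 4, asks whether the platelet phenotype of PAD patients associates with measures of cognitive impairment. Participants are to be tested remotely "using the MoCA and/or TICS tests", and the analysis is one sentence: "We will correlate these measures with already collected platelet activity measures". Appendix A, item 5.7, has the cognitive test done once.

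Aims 1 and 2 are worded differently. Aim 1 uses Cox models to "determine the independent association of the platelet phenotype with risk of cardiovascular events in the first 30 days after surgery", and Aim 2 also asks for an independent association.

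Section 8.1 covers Aims 1 and 2 by name and has a sentence on mRNA-miRNA pairs. It mentions neither Aim 4 nor cognition. It extends the plan to secondary outcomes, with major bleeding as the only example.

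The background reports that platelet activation markers are often abnormal in Alzheimer's disease "when compared with age-matched cognitively normal controls". It also cites a cohort result in which platelet aggregation was "independently associated to the risk of incident dementia even after adjusting for potential confounders".

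**The concern.** Cognitive scores commonly depend on age, and platelet measures may. Section 4.g admits anyone over 21 with no upper limit, so age can vary widely in the cohort. If age is related to both variables, a plain correlation mixes any platelet-cognition link with the part that runs through age. It can show an association where there is none, or cancel one that exists. A reader of the Aim 4 result could not tell which had happened, and the result could not be set beside the adjusted evidence that the background uses to justify the aim.

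**Working it through.** **Text check.** The documents give no sample size, power or effect size for Aim 4, so there is no planned figure to reproduce. The places where age, matching or adjustment appear are:

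| Place | What it covers | Does it adjust Aim 4? |
|---|---|---|
| Background on platelets and dementia | Age-matched controls and a confounder-adjusted cohort result, both earlier work | No |
| Section 4.f | Participants' age, as the reason for asking about a dementia diagnosis before consent | No |
| Section 8, power paragraph | Age- and sex-matched controls in a comparison of CVD with controls | No |
| Section 8.1 | Independent association for Aims 1 and 2; sociodemographic and clinical factors compared by cardiovascular event status | No |

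Age should be available: section 4.b has staff "review the clinical history, demographic information, diet questionnaire, lifestyle assessment", and Appendix A lists demographics before surgery.

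**Illustration 1: no true link.** All inputs are assumed. The sample size of 160 is also illustrative: 350 x 0.65 alive x 0.70 tested = 159.

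The correlation produced by age alone is r = r(age, platelet) x r(age, cognition). The two-sided 5% rejection rate by Fisher z is Φ(m - 1.96) + Φ(-m - 1.96), with m = |atanh r| x √(n - 3).

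Strong end: r = 0.3 x (-0.5) = -0.15 and |atanh r| = 0.1511.
- n=100: m = 0.1511 x √97 = 1.489; rate = Φ(-0.471) + Φ(-3.449) = 0.319.
- n=160: m = 0.1511 x √157 = 1.894; rate = Φ(-0.066) + Φ(-3.854) = 0.474.

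The adjusted rates come from simulated regressions of cognition on platelet measure, age, sex and years, with 10,000 studies per setting.

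| r(age, platelet), r(age, cognition) | Spurious r | Plain, n=100 | Plain, n=160 | Adjusted, n=100 / n=160 |
|---|---|---|---|---|
| 0.1, -0.3 | -0.03 | 6.0% | 6.6% | 5.2% / 4.8% |
| 0.2, -0.4 | -0.08 | 12.4% | 17.1% | 5.0% / 4.8% |
| 0.3, -0.5 | -0.15 | 31.9% | 47.4% | 4.8% / 5.2% |

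**Illustration 2: true link hidden.** Assume an age-adjusted platelet slope of -0.20 SD, with platelet activity falling as age rises. Age's own slope is b = r(age, cognition) + 0.20 x r(age, platelet), and the plain correlation is -0.20 + b x r(age, platelet). For -0.3 and -0.5: b = -0.5 - 0.06 = -0.56, so plain r = -0.20 + 0.168 = -0.032. The power figures are simulated.

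| r(age, platelet), r(age, cognition) | Plain r | Power n=100, plain / adjusted | Power n=160, plain / adjusted |
|---|---|---|---|
| -0.1, -0.3 | -0.168 | 39% / 54% | 57% / 75% |
| -0.2, -0.4 | -0.112 | 20% / 57% | 29% / 77% |
| -0.3, -0.5 | -0.032 | 6% / 59% | 7% / 80% |

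**Cost of adjusting.** True slope -0.20 SD, simulated.
- Age unrelated to both variables: power goes from 51.6% to 50.1% at n=100 and from 72.8% to 72.1% at n=160.
- Age related to platelet activity (r = 0.3) with no effect of its own on cognition: from 52% to 47% at n=100 and from 72% to 67% at n=160.

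**The case against.** The strongest reply is that this is silence in an incomplete text. The power paragraph in section 8 stops mid-sentence. Readable section 8.1 contains no Cox or multivariable text even for Aims 1 and 2, where an independent association is promised. Correlate is also a loose verb in an aims paragraph. This stands: a reader might infer that the investigators decided against adjustment, and the documents do not support that.

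Second, Aim 4 asks only whether the phenotype associates with impairment, and the background and section 5.1 speak of detecting or predicting risk. For a marker question an unadjusted association is a legitimate first estimate. So a reader should not infer that separating platelet from age effects is the stated purpose of Aim 4. What remains is that a marker's value over and above age would still matter, and that the motivating cohort result was adjusted.

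Third, the figures are hypothetical. Even the sign of the age-platelet relation is unknown, and at the weak end the excess is 6% against 5%. This also stands; the tables show what could happen, not what will.

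Fourth, section 8.1 does plan to examine sociodemographic and clinical factors, and its extension to secondary outcomes is not an exclusive list. Neither clearly reaches cognition. Even if the extension did, the visible steps are univariate analyses and comparisons by event status, with no covariate list.

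**Conclusion.** The point holds in a limited form. The one analysis stated for Aim 4 is a correlation, no readable text adjusts it for age, and a better analysis is available at small cost. Adjustment is unstated, not excluded.

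Under the assumed inputs, the false-positive rate of the plain correlation runs from barely above 5% to about a third (n=100) or nearly half (n=160). With the opposite age-platelet sign, its power can fall to 6% or 7%. None of these inputs is in the documents. Adjustment removes the part due to measured age; it does not deal with unmeasured confounders. This is a change that should be made, not a flaw that invalidates the study.

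Two further inferences should be avoided. Participants who died, declined, lacked capacity or were not reached might be thought only to weaken a true association. The documents do not support one direction: death may depend on platelet activity, which is Aim 2's own hypothesis, so losses could bias the association either way. The choice of test, platelet measure and sampling time might be read as a multiplicity error. It is missing detail: the background speaks of testing "with 2 previously validated neuropsychiatric tests that are frequently used in aging studies" while Aim 4 leaves the choice open, and the co-primary platelet measures in section 8 are set for short-term events.

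**What to change.** In Aim 4 and section 8.1, state that the main analysis is a regression of the cognitive score on the platelet measure, adjusted for age, sex and years from platelet sample to cognitive test. Add education if it is recorded; the documents do not name it, and one question in the same call would supply it. Report the plain correlation as descriptive. If a covariate list already exists in text that is not readable here, a cross-reference from Aim 4 is enough.

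Optional: name one cognitive test, one platelet measure and one sampling time as primary, since section 4.c plans "Blood collection at three different time points", and label the other pairings secondary.

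The cost is analysis-plan wording, slightly more analysis work and a few degrees of freedom. The power loss is about 1 point if age is unrelated to both variables. It reaches about 4 to 5 points if age tracks platelet activity (r = 0.3) but has no effect of its own on cognition, which is an unlikely combination.

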Following the interview and signed informed consent, subjects will have their blood drawn, and will be asked to provide a urine sample prior to surgery. Blood will be obtained from the patient using standard aseptic phlebotomy techniques. Blood will be collected from an arterial line placed for surgery (if available) or at the time of the intravenous line being placed for surgery or using a standard technique of blood drawing. A brief description of the standard technique follows: after cleansing of the venipuncture site with an alcohol wipe and removal of excess alcohol with sterile gauze, a tourniquet will be applied to the patient's bicep region. A 19G or 21G butterfly needle will be inserted into the antecubital vein, the tourniquet will be removed, and free-flowing blood will be collected with minimal trauma and stasis. The needle will be removed when blood collection is complete and sufficient pressure will be applied using sterile gauze at the puncture site until cessation of bleeding. A sterile band-aid will be applied to cover the venipuncture site. For each patient, no more than 60 ml (≈4 table spoons) of blood will be collected in gold (serum separator tube) top, lavender (EDTA anticoagulant) top, green (heparin), blue (sodium citrate anticoagulant) top and Pax gene tubes. Approximately 40 cc of blood will be used for the different measurements of platelet function, inflammation, coagulation and other biomarkers of cardiovascular risk and approximately 20 cc of blood will be used to purify platelet RNA, whole blood RNA and DNA and then stored in -80C for the RNA, microRNA, and DNA profiling. The samples will be placed in the PI's lab at NYU New Science Building- Cardiology 7th floor without any identifying information other than a code number. The code number will not be based on any information that could be used to identify the subject (for example, social security number, initials, birth date, etc). The master list linking names to code numbers will be kept in a locked file cabinet, separate from all research information in the PI's office at NYU Skirball 9th floor and will be accessed by the PI. The urine specimen will be collected to measure abnormalities in thrombosis, hemostasis and inflammation as well. At the end of the patient recruitment and measurement of platelet function (probably within 4 years time), based on ones level of platelet activity, thrombin generation, coagulation and inflammation we will measure RNA, microRNA, and DNA in patients with different phenotypes of vascular disease, markers of thrombosis/hemostasis, and events from the stored specimens.

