The blood specimen will be analyzed upon completion of the study for mRNA, microRNA, and DNA profiling. We will perform detailed molecular profile study, describing genetic arrays with different phenotypes associated with platelet activity. We will be looking at specific transcripts associated with thrombotic and/or bleeding outcomes and different cardiovascular diseases. Platelet-rich plasma (PRP) will be isolated for platelet purification and subsequent genetic analysis will be performed. We will be analyzing those with high and low levels of platelet activity and other cardiovascular biomarkers as well as those with clotting/no clotting or bleeding/no bleeding. Biomarkers of cardiovascular disease will be shared as per NIH. The samples will be stored in the PI's lab, NYU New Science Building- Cardiology 7th floor, without any identifying information other than a unique code number. The code number will not be based on any information that could be used to identify the subject (for example, social security number, initials, birth date, etc.). The master list linking names to code numbers will be kept in a locked file cabinet, separate from all research information. Biomarker testing is separate from genetic testing. Genetic information will not be disclosed to anyone, including the participants and their physicians. Positive test result can be an indication that the individual may be predisposed to high platelet activity associated with peripheral vascular disease. There is no need for independent testing since patients are already diagnosed with this condition. No tests other than authorized shall be performed on the biological sample. Samples shall be destroyed at the end of the testing process.

e. Future Sample Storage

All patients will be offered an option to have their blood stored for future processing. If a patient does not agree to store his/her blood for future tests not related to this study, then his/her blood will be destroyed after all planned laboratory tests have been performed.

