To ascertain vital status, we may use the social security index, medical record chart review, or contact the participant directly. If we learn that the participant is deceased, we may perform a chart review to check for any prior clinical diagnosis of cognitive impairment.

We will seek remote verbal re-consent for sub-clinical cognitive function testing (via TICS and/or MoCA test) from all living study participants. We will document in the study record whether a participant consents or declines to participate in the cognitive function testing. For participants who provide verbal consent, testing will be administered remotely by trained study personnel and will not require any in-person visits. If we identify sub-clinical signs of cognitive impairment based on testing, we will inform the patient and will offer them the possibility of writing a letter to their primary healthcare provider.

Participants with existing mild cognitive impairment: Given the advanced age of study participants, we will first ask participants if they have ever been diagnosed with dementia (including Alzheimer's) by their healthcare provider and record their response in the study record. In collaboration with the PI, our neuroscience experts, and our senior research coordinator, we will assess decision-making capacity while talking to the participant. If the participant has sufficient capacity to consent, we will proceed with seeking verbal consent for cognitive function testing. If the participant declines cognitive function testing but gives permission for us to record their history of cognitive impairment, we will record this information in the study record. If the participant appears unable to provide verbal consent, they will not undergo cognitive function testing.

g. Inclusion Criteria

1. Subjects undergoing non emergent lower extremity revascularization*
2. Age > 21 years of age

3. Able and willing to provide written informed consent for the study

*Subjects who participated in this trial may be re-enrolled if they undergo another lower extremity revascularization >90 days after the original procedure. *This modification is being done to increase enrollment and because the major aim is to look at peri-procedural events and thus would not interfere with the overall goal of the study.*

h. Exclusion Criteria

1. Use of any NSAID (ibuprofen, naproxen, etc.) within 72 hours
2. Thrombocytopenia (platelet count<100) or Thrombocytosis (platelet count>500)

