8.1 Data Analysis

All eligible subjects will be assigned a unique identification number upon enrollment in the study. Initial study data will be recorded on a printed form, which will be later converted to an IRB approved electronic database, REDCap. Only study personnel will have access to this database. All potential identifiers will be kept separately in a safe location at the PI's office in NYU Skirball 9th floor, where it will be placed under double lock and key and the PI will have access. After verification of entered data at completion of the study all potential identifiers will be stripped from the database.

Descriptive statistics, including frequency tables, measures of center and variability, and graphical displays will present baseline subject characteristics. Similar analyses will present values of platelet activity measures.

Primary Platelet Activity Measures: LTA and MPA To test the hypothesis that platelet activity measurements are independently associated with 30-day (Aim 1) and long-term (Aim 2) cardiovascular events in patients undergoing lower extremity revascularization we will employ the following analysis. For Aim 1, platelet activity will be measured preoperatively and the main outcome will be 30-day cardiovascular events. For Aim 2, platelet activity will be measured 48 hours postoperatively and the main outcome will be long-term (mean follow-up ~ 2 years) cardiovascular events. We will perform univariate analysis to investigate the association between LTA and MPA platelet activity measures and cardiovascular events. Next, we will examine differences in sociodemographic/clinical factors between participants with and without a cardiovascular event using two-sided tests of proportions for categorical variables (chi-square, Fisher's exact) and t-tests or non-parametric alternatives (e.g., Wilcoxon test) for continuous measures.

The analysis plan outlined above for the primary platelet activity measures will be applied to the set of secondary measures including thrombin. In addition, the analysis plan outlined above for the primary outcome measures will be applied to the secondary outcome measures including major bleeding.

To identify novel mRNA-miRNA target pairs involved in platelet activation, we will computationally inversely correlate miRNA expression with expression of gene targets using established prediction databases

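### Aim 3 does not say how antiplatelet therapy is handled when high and low platelet-activity groups are selected and compared, so mixed drug exposure may confound the RNA and microRNA contrast.

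*Combined protocol and SAP*

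**What the plan says.** Aim 3 (section 3) is "To investigate mRNA-microRNA co-expression profiles in patients with and without elevated platelet activity measurements". Section 4.c places the choice of samples at the end of recruitment: "based on ones level of platelet activity, thrombin generation, coagulation and inflammation we will measure RNA, microRNA, and DNA". Section 4.d then states the comparison: "We will be analyzing those with high and low levels of platelet activity and other cardiovascular biomarkers". Both 4.c and 4.d also bring in patients with and without events. No cut-off, assay or time point is given for high and low in Aim 3. Section 8.1 does name the main assays for the study as a whole: "Primary Platelet Activity Measures: LTA and MPA".

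The only Aim 3 analysis described in section 8.1 is that "we will computationally inversely correlate miRNA expression with expression of gene targets using established prediction databases". No covariate is mentioned there. An independent association is promised for Aims 1 and 2 only.

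The one exclusion based on a drug is in section 4.h: "Use of any NSAID (ibuprofen, naproxen, etc.) within 72 hours". No criterion or procedure mentions antiplatelet drugs or a washout. The baseline interview (section 4.b) covers "lifestyle assessment, medication use and adherence, with the individual". Appendix A lists medication use at every time point and adherence at the pre-operative, post-operative appointment and long-term contacts.

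**The concern.** An antiplatelet drug is given to lower platelet activity. If some patients take one and others do not, or regimens differ in strength, choosing patients by measured activity tends to put the more strongly treated in the low group and the less treated in the high group. A transcript that responds to the drug, or that goes with the reason for prescribing it, can then differ between groups without having any part in platelet activity.

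Aim 3 is meant to yield diagnostic markers and possible treatment targets. Some candidates could therefore be markers of treatment. The information needed to guard against this is already on the case report form, but no use of it in Aim 3 is stated.

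**Working it through.** The plan gives no sample size, power, drug frequency or drug effect for Aim 3, so there is no figure of its own to reproduce. The check asks how far a drug-blind split would unbalance the groups, and how much of the high-low gap the drug would then explain.

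**Assumptions (none is in the documents).** A share p of patients is on drug. Measured activity is Y = U − d·D, where U is standard Normal, D = 1 on drug and 0 otherwise, and d is the drug effect in within-group SDs. U and D are independent. Low and high are the bottom and top tertiles.

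**Formulas.**
- The tertile cuts a and b solve (1−p)Φ(c) + pΦ(c+d) = 1/3 and 2/3.
- Share on drug in the low group = 3pΦ(a+d); in the high group = 3p[1 − Φ(b+d)].
- Drug's share of the gap = d × (low share − high share) / (mean Y in high − mean Y in low).

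**Worked case, p = 0.5, d = 1.** The cuts are a = −0.988 and b = −0.012. Low: 1.5 × Φ(0.012) = 1.5 × 0.505 = 0.76. High: 1.5 × [1 − Φ(0.988)] = 1.5 × 0.162 = 0.24. The gap in mean activity is 2.45, so the drug's share is 1 × 0.515 / 2.45 = 21%.

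| p | d | On drug, low | On drug, high | Difference (points, unrounded shares) | Gap | Drug's share of gap |
|---|---|---|---|---|---|---|
| 0.3 | 0.5 | 42% | 19% | 22.5 | 2.24 | 5% |
| 0.5 | 1 | 76% | 24% | 51.5 | 2.45 | 21% |
| 0.5 | 1.5 | 86% | 14% | 71.8 | 2.76 | 39% |
| 0.5 | 2 | 93% | 7% | 86.4 | 3.16 | 55% |
| 0.8 | 1 | 94% | 62% | 32.1 | 2.35 | 14% |
| 0.9 | 1 | 97% | 80% | 17.7 | 2.27 | 8% |
| 1.0 | any | 100% | 100% | 0 | 2.18 | 0% |

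**When would the drug dominate?** Its share of the total variance is R² = p(1−p)d² / [1 + p(1−p)d²]. This reaches one half when d = 1/√(p(1−p)): 2.0 SD at p = 0.5, 2.5 SD at p = 0.2 or 0.8, and 3.3 SD at p = 0.9.

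**What smaller imbalances can do.** Take a transcript unrelated to U that the drug or its indication shifts by 1 SD (again an assumption). The expected false difference between groups equals the imbalance: 0.23 SD at p = 0.3, d = 0.5; 0.51 SD at p = 0.5, d = 1; 0.18 SD at p = 0.9, d = 1. Confounding therefore does not require the drug to dominate the split.

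**Is there overlap for adjustment?** Suppose both outer tertiles of the planned 350 were profiled, 350/3 ≈ 117 per group. At p = 0.5, d = 1, about 0.243 × 117 ≈ 28 in the high group are on drug and, by symmetry, about 28 in the low group are off it. At p = 0.5, d = 2 the number is 0.068 × 117 ≈ 8.

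**The case against.** The strongest reply is that the documents do not show the groups to be sorted by drug. A reader might infer that the comparison mainly separates drug regimens and not platelet biology. The documents do not support that: they name no antiplatelet drug in the body of the plan, give no frequency or effect, and do not state that measurements are taken on treatment; that is inferred from the absence of any washout or exclusion. In the table the drug passes half of the gap only at a 2 SD effect with use evenly split. With near-universal use of a single regimen the imbalance shrinks towards zero, although the two-level model ignores differences in agent and dose. This part of the reply stands.

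A reader might also infer that later analysis could not repair a drug-blind selection. That is too strong. Medication use is recorded, selection also runs on events, and the groups overlap on drug at moderate effects. Overlap becomes thin only at large effects. Nor should the NSAID exclusion be read as the plan recognising assay interference: section 4.h gives no reason, and a bleeding rationale fits equally well.

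Four further points deserve weight.
- The assay is not fixed for Aim 3, and LTA and MPA need not respond equally to a drug.
- Activity measured despite therapy is a legitimate phenotype, and grouping only within regimen would change the question. That is a reason not to abandon the raw contrast.
- The power paragraph in section 8 and the Aim 3 sentence in 8.1 break off in the text available to me, so wording on adjustment may have been lost.
- Section 2 describes platelet characterization as already done, so the profiling samples may already be chosen.

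None of this removes the core point. The selection rule is stated in three places, and each is silent on antiplatelet drugs.

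**Conclusion.** The point holds as a gap with a plausible, unquantified bias. If antiplatelet exposure is mixed, the selection rule as written leaves the Aim 3 groups unbalanced on it, and no visible analysis step accounts for this.

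Over the three reference scenarios (p = 0.3, d = 0.5; p = 0.5, d = 1; p = 0.9, d = 1) the low and high groups differ by roughly 18 to 51 percentage points in drug use, while the drug explains about 5% to 21% of the gap in activity. These figures rest on an assumed tertile split, a two-level exposure, a Normal marker, and values of p and d that the documents do not supply. They support calling the drug a confounder to be handled, and go no further. If all patients have the same exposure, the problem does not arise. It concerns Aim 3 only, and the change should be made because it is cheap and uses data already planned.

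**What to change.** In sections 4.d and 8.1:

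- Include the antiplatelet regimen recorded at the time of the sample as a covariate in the differential-expression and miRNA-mRNA models.
- Report a sensitivity analysis within regimen beside the main contrast.
- If samples have not yet been chosen, balance or stratify the high/low selection by regimen, pooling small strata. If they have been chosen, the first two steps still apply.
- State the assay, time point and cut-off that define high and low, since the drug effect may depend on them.

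The cost is a few sentences of protocol text, some loss of precision from the extra covariate and, if selection is stratified, a slightly less extreme raw contrast. Small strata will limit the within-regimen analysis. No new data are needed, and nothing about patients' treatment changes.
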